15.0 Confidentiality, Privacy, and Data Security

15.1 PROTECTING PRIVACY: Indicate how subject privacy will be protected:

- Conduct conversations about the research in a private room
- Ask the subject how they wish to be communicated with – what phone numbers can be called, can messages be left, can they receive mail about the study at home, etc.
- Take special measures to ensure that data collected about sensitive issues do not get added to their medical records or shared with others without the subject's permission
- Other methods (describe below)

15.2 SENSITIVE DATA: Do any of the instruments ask about illegal or stigmatized behavior:

Yes No

15.3 SIGNIFICANT CONSEQUENCES OF A LOSS OF PRIVACY OR CONFIDENTIALITY: Could a breach of privacy or confidentiality result in any significant consequences to participants, such as criminal or civil liability, loss of state or federal benefits, or be damaging to the participant's financial standing, employability, or reputation:

Yes No

Check all that apply:

- Embarrassment
- Criminal or civil liability
- Loss of state or federal benefits
- Damaging to the participant's financial standing, employability, or reputation
- Potential risks to insurability (health, disability, or life insurance)

Describe the potential consequences:

Loss of privacy may result in recognition of an individual or a family, or that an individual or family are from a particular ethnicity or cultural group. Loss of privacy may occur from publication of a family pedigree or a photograph or through identification of a participant from genetic data deposited into a shared scientific database. This may conceivably lead to stigmatization or to discrimination regarding healthcare or insurance, although the chances of this happening are very small. We are almost always able to share papers that are being written with the family prior to submission to a journal so that they are comfortable with the submitted material.

15.4 EXTRA CONFIDENTIALITY MEASURES: Explain any extra steps that will be taken to assure confidentiality and protect identifiable information from improper use and disclosure, if any:

We are almost always able to share papers that are being written with the family prior to submission to a journal so that they are comfortable with the submitted material. We would discuss modifying papers prior to submission if the family indicated that they felt uncomfortable.

15.5 * REPORTABILITY: Do you anticipate that this study may collect information that State or Federal law requires to be reported to other officials, such as elder abuse, child abuse, or threat to self or others: (REQUIRED)

Yes No

15.6 CERTIFICATE OF CONFIDENTIALITY: Will this study obtain a Certificate of Confidentiality:

Yes No

Please include the recommended Certificate of Confidentiality language in the consent form.

15.7 SHARING OF RESEARCH RESULTS: Will there be any sharing of **EXPERIMENTAL research test results with subjects or their care providers:**

Yes No

Note: This is unusual and not recommended, particularly in cases where the tests are carried out in a non-CLIA certified laboratory, the results are of unproven clinical significance, or where there are not known preventative strategies and/or treatments. If these are the most likely scenarios for your study, you should check 'No.'

If you have an incidental finding of clear clinical significance, call the HRPP QIU at [contact] for a consult.

Explain under what circumstances research results may be shared:

We will be providing exome sequencing results to the participants and their health care providers from this study. Families will decide if they wish to receive secondary findings unrelated to the indication for exome sequencing at the time of the consent process.

Both parents, when present as part of the biological trio, must agree to hear about secondary findings, or these will not be returned. These results will not be included in the medical records of the parents. We will not be releasing results such as APOE4 and Huntington's, as there are no definitive treatments available. For secondary findings that relate to adult onset disorders, we will report them and include them even if the child is not 18 years of age. Children may leave the area and not be traceable if the results are not released, and they cannot be stored without confidentiality risks.

15.9 * HIPAA APPLICABILITY: Study data will be: (REQUIRED)

- Derived from a medical record (e.g. APeX, OnCore, etc. Identify source below)
- Added to the hospital or clinical medical record
- Created or collected as part of health care
- Used to make health care decisions
- Obtained from the subject, including interviews, questionnaires
- Obtained ONLY from a foreign country or countries
- Obtained ONLY from records open to the public
- Obtained from existing research records
- None of the above
- Derived from the Integrated Data Repository (IDR) or The Health Record Data Service (THREDS) at SFGH

In addition to signing a consent form, each subject will have to sign the UCSF Research Subject Authorization Form (HIPAA Form).

Upload the HIPAA Authorization Form in the Other Study Documents section of the Initial Review Submission Packet Form.

Failure to have patients sign the HIPAA Authorization is one of the most common findings from QIU Routine Site Visits. Please call the IRB office at [contact] if you have questions about HIPAA research requirements.

If derived from a medical record, identify source:

UCSF medical record or other patient medical record

15.10 * IDENTIFIERS: Check all identifiers that will be collected and included in the research records, even temporarily: (REQUIRED)

- Names
- Dates
- Postal addresses (if only requesting/receiving zip codes check Yes to the Zip Code question below instead of checking this box)
- Phone numbers
- Fax numbers
- Email addresses
- Social Security Numbers*
- Medical record numbers
- Health plan numbers
- Account numbers
- License or certificate numbers
- Vehicle ID numbers
- Device identifiers or serial numbers
- Web URLs
- IP address numbers
- Biometric identifiers
- Facial photos or other identifiable images
- Any other unique identifier
- None

* Could study records include ANY photos or images (even 'unidentifiable' ones): **(REQUIRED)**

Yes No

15.11 * ZIP CODES: Some research data sets include zip codes. Will you be receiving data with zip codes as the only portion of an address: (REQUIRED)

Checking 'Yes' here means that you will not be requesting access to any other data element of a patient's address. If you are requesting other parts of an address such as street names and address numbers, check 'No' here and check the box for 'Postal addresses' in the list of 18 PHI Identifiers in the previous question.

Yes No

15.12 * PATIENT RECORDS: Will health information or other clinical data be accessed from UCSF Health, Benioff Children's Hospital Oakland, or Zuckerberg San Francisco General (ZSFG): (REQUIRED)

Yes No

15.13 * CLINICAL DATA - GENERAL DESCRIPTION: Provide a general description of the types of clinical data that you are requesting access to: (REQUIRED)

We have requested access to patients' medical entire medical records because data regarding the patient's medical history and phenotype is required by the laboratory in order to inform the

analysis of exome data, allows us to learn about the natural history and phenotypes of very rare conditions as part of this research study, and is also needed to assess the clinical utility of exome sequencing, which is a major focus of this study.

15.14 * CHART/CLINIC NOTES AND OTHER FREE TEXT FIELDS: Will the medical record data include any information extracted from free text fields: (REQUIRED)

Yes No

Data sets that include free text from fields such as chart notes, clinic notes, and other text fields are considered identifiable, even without direct identifiers.

15.15 * HIPAA - PERMISSION TO ACCESS SENSITIVE DATA: Does the research require access to any of the following types of health information from the medical record: (check all that apply) (REQUIRED)

- Drug or alcohol abuse, diagnosis or treatment
- HIV/AIDS testing information
- Genetic testing information
- Mental health diagnosis or treatment
- None of the above

Important note: Ensure that participants initial the corresponding line(s) in Section C of the HIPAA authorization form during the consent process.

15.16 * ACCESS TO OTHER SENSITIVE OR PROTECTED DATA: Are you requesting access to any sensitive health data not protected under HIPAA (any other health history that patients would expect to be kept private such as records relating to treatment for obesity, STDs, compulsive behaviors, embarrassing health conditions, sexual orientation and practices, etc.): (REQUIRED)

Yes No

* List the types of sensitive data and provide a scientific justification to support the request. The IRB may require additional safeguards to protect the confidentiality of participants: (REQUIRED)

Some types of sensitive information may be utilized to help identify a diagnosis through exome sequencing. For example, we summarize the patient's phenotype for the laboratory so that it can inform their analysis of the exome data and so if they identify a genetic variant that may be diagnostic, they will be able to ascertain whether the associated phenotype fits with our patient's phenotype and the expected inheritance pattern. Such sensitive information could include descriptions of psychiatric symptoms that may be suggestive of a specific genetic condition, or consanguinity (which suggests that the lab should be looking for variants in genes associated with autosomal recessive conditions).

15.18 * IDENTIFIABILITY OF FINAL DATA SET: (REQUIRED)

Which type of data set are you requesting IRB approval for:

A de-identified data set does not include ANY of the 18 HIPAA identifiers in the list above or any free text fields.

A limited data set (LDS) is described as health information that excludes direct identifiers but that may include:

- City
- State

- ZIP Code
- Elements of date (including dates such as admission, discharge, service, month and year)
- Other numbers, characteristics, or codes not listed as direct identifiers, including ages in years, months or days or hours

Identifiable data sets include direct identifiers and/or information from free text fields.

Review the [HIPAA FAQs on the IRB website](#) for more details about identifiability of data sets.

- De-identified data set
- Limited data set
- Identifiable data set without direct identifiers (includes free text fields)
- Identifiable data set with direct identifiers (may or may not also include free text fields)

15.19 * DATA COLLECTION AND STORAGE: (check all that apply): (REQUIRED)

Collection methods:

- Electronic case report form systems (eCRFs), such as OnCore or sponsor-provided clinical trial management portal
- UCSF ITS approved Web-based online survey tools: Qualtrics or RedCap
- Other web-based online surveys or computer-assisted interview tool
- Mobile applications (mobile or tablet-based)
- Text Messaging
- Wearable devices
- Audio/video recordings
- Photographs
- Paper-based (surveys, logs, diaries, etc.)
- Other:

*** What online survey or computer assisted interview tool will you use: (REQUIRED)**

- Qualtrics (Recommended)
- RedCAP (Recommended)
- Survey Monkey (NOT recommended and may require UCSF ITS Security review)
- Other

*** Data will be collected/stored in systems owned by (check all that apply): (REQUIRED)**

- Study sponsor
- UCSF data center (including OnCore, RedCap, Qualtrics, and MyResearch)
- UCSF encrypted server, workstation, or laptop residing outside of UCSF data center
- Personal devices, such as laptops or tablets that are not owned or managed by UCSF
- SF VAMC
- Zuckerberg San Francisco General Hospital
- Benioff Children's Hospital Oakland
- Langley Porter Psychiatric Institution
- Other UCSF affiliate clinic or location (specify below)
- Cloud vendor such as Amazon Web Services (AWS), Salesforce, etc. (specify below)
- Other academic institution
- 3rd party vendor (business entity)
- Other (explain below)

* Provide more details about where study data will be stored: **(REQUIRED)**

Secure UCSF Box folders, which are HIPAA compliant.

15.20 * ADDITION OF RECORDS TO A REGISTRY: Will patient records reviewed under this approval be added to a research database, repository, or registry (either already existing or established under this protocol): (REQUIRED)

Yes No

This activity generally requires patient consent and HIPAA Authorization. A Waiver of Consent/Authorization may be granted for patients who are deceased or lost to follow up, but ongoing patients should be consented at their next clinic visit prior to accessing their health records or they may provide consent and HIPAA authorization for research use of their health information by mail or through a certified E-Signature system such as DocuSign. You may be asked to revise your consent plans.

15.21 * DATA SHARING: During the lifecycle of data collection, transmission, and storage, will identifiable information be shared with or be accessible to anyone outside of UCSF: (REQUIRED)

Yes No

16.0 Financial Considerations

16.1 * PAYMENT: Will subjects be paid for participation, reimbursed for time or expenses, or receive any other kind of compensation: (REQUIRED)

Yes No

16.2 PAYMENT METHODS: Subjects payment or compensation method (check all that apply):

Payments will be (check all that apply):

- Cash
- Check
- Gift card
- Debit card
- UCSF Research Subject Payment Card
- Reimbursement for parking and other expenses
- Other:

16.3 PAYMENT SCHEDULE: Describe the schedule and amounts of payments, including the total subjects can receive for completing the study:

- **If there are multiple visits over time, explain how payments will be prorated for partial completion**
- **If deviating from recommendations in Subject Payment Guidelines, include specific justification below**

Subjects who complete the return of results survey will receive a \$20 gift card to Safeway or Target as a thank you gift for their time. Subjects who complete the survey for the 5-7 month follow-up visit will receive a \$30 gift card to Safeway or Target. The gift cards are per family, so

one parent will be asked to complete the surveys on behalf of the family. Most families will have the opportunity to complete surveys and receive the gift cards, however some families (approximately 70) who agreed to be interviewed by our ethics (ELSI) team will not be asked to do surveys and will receive gift cards as part of the separate ELSI study IRB protocol for participating in interviews.

16.4 COSTS TO SUBJECTS: Will subjects or their insurance be charged for any study activities:

Yes No

Describe the costs that may be incurred by subjects or 3rd party payers as a result of participation:

- Explain why it is appropriate to charge those costs to the subjects
- If this is a therapeutic study, compare subjects' costs to the charges that would typically be associated with receiving care off-study (e.g. is it more expensive to participate in this study than to receive care off-study?)

Insurance will be billed for patient visits, as the visits are part of standard care. Consent and follow-up will be conducted when patients are seen during routine clinical visits.

17.0 Other Approvals and Registrations

17.1 * ADMINISTRATION OF RECOMBINANT DNA: Does this study involve administration of vaccines produced using recombinant DNA technologies to human subjects (Help Link added Aug '15): (REQUIRED)

Yes No

17.2 * HUMAN GENE THERAPY: Does this study involve human gene therapy: (REQUIRED)

Yes No

17.4 OTHER APPROVALS: Indicate if this study involves other regulated materials and requires approval and/or authorization from the following regulatory committees:

Institutional Biological Safety Committee (IBC)

Specify BUA #:

Institutional Animal Care and Use Committee (IACUC)

Specify IACUC #:

Controlled Substances

Clinical Utility of Pediatric Whole Exome Sequencing  
NCT03525431  
Document Date: 02/09/2022

Statistical analysis plan: Our study design will allow statistical comparisons that will generate useful data regarding WES implementation. Diagnostic yield will be calculated per case for the proband. It will be based on the number of cases with a positive or likely positive exome result divided by the total number of cases. The size of the “positive” (likely positive or probable positive), “inconclusive” or “negative” groups will depend on the diagnostic success rate of WES in our cohort. We will conduct analysis to determine how clinical utility (measured as diagnostic yield) may vary based on a number of factors, including setting (prenatal or pediatric), by disease indication, by race/ethnicity, and by socioeconomic status. Such stratified analyses will depend on the actual observed sample sizes within each stratum.

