7.0 Research Plan and Procedures

7.1 HYPOTHESIS: Describe the hypothesis or what the study hopes to prove:

We hypothesize that next-generation sequencing studies, such as whole exome sequencing, will have clinical utility in patients with medical conditions that have a genetic etiology.

7.2 AIMS: List the specific aims:

(1) To determine the clinical utility of whole exome sequencing in the minority and underserved population at 6 months after whole exome sequencing. We will recruit and consent up to 800 Pediatric patients and biological parents with a variety of indications, including intellectual disability, seizures, encephalopathy, metabolic disease, birth defects, neurodegenerative conditions and multiple congenital anomaly syndromes. We will perform whole exome sequencing and provide a result(s) to the family. Results will be defined as:

1. Results of diagnostic or medical importance in relation to the probands presenting condition or the reason for the test;
and, 2. Secondary or additional findings that are deemed relevant to the health of the patient or parents and that will be reported out to the participants and/or their primary physician. These secondary results can include any other result that the study team determines that is of medical importance and must be reported to the participant and/or their primary physician.

We will use the American College of Medical Genetics and Genomics published list of 59 genes that are considered medically actionable: <http://www.nature.com/gim/journal/v19/n2/full/gim2016190a.html>

For genes that are not on this list and that may be considered actionable, the sign-out team will need to be in consensus that: 1) the sequence variant to be reported is either pathogenic or likely pathogenic; and 2) the gene is medically actionable. If there is any controversy, a specialist in the relevant clinical area will be consulted regarding actionability of the gene.

After 6 months, we will see the families in follow up and assess clinical utility.

We will recruit patients from UCSF Mission Bay, UCSF Oakland and Zuckerberg San Francisco General Hospital and UCSF Fresno/Community Medical Center.

7.3 DESIGN: Briefly describe the study design (e.g., observational, interventional, randomized, placebo-controlled, blinded, cross-over, cross-sectional, longitudinal, pharmacokinetic, etc.):

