This study aims to recruit and consent patients and biological family members who have at least one individual with a medical condition that is likely to have a genetic etiology. We will study the clinical utility of exome sequencing in underserved and underrepresented minority populations. To do this, we will perform whole exome sequencing as a test to generate sequence data in order to determine the genetic etiology of the medical condition. Families will undergo questionnaires and interviews to determine the clinical utility of exome sequencing for their healthcare. The medical providers involved in the study will also undergo questionnaires to determine if the exome sequencing has had clinical utility for their patient. The sequence variant data from the exome sequencing will be studied as part of research be sent to the National Institutes of Health for sharing in databases such as dbGAP and ClinVar, in accordance with current NIH policy. We will share sequence variants in the form of .vcf files and phenotype data in pedigree form that enables relationships between proband and other relatives to be determined. Data will be available for broad use that is not limited to specific diseases.

7.4 BACKGROUND AND SIGNIFICANCE: Briefly provide the background and significance of this study (e.g. why is this study needed) (space limit: one half page):

If this is a first in humans study, please summarize the safety data from the animal studies. For pediatric drug or device studies, please identify if this is the first study in pediatric populations.

Congenital abnormalities and developmental disorders affect 3-5% of live born infants and children. Despite advances in both pre- and post-natal treatment, the utility of genetic testing in diagnosing the etiology underlying such conditions in order to guide management has been frustratingly limited. Traditional genetic testing with specific gene tests, or even gene panels, is diagnostic in only a small percentage of cases. Recent technological advances in next generation sequencing (NGS) have led to the ability to sequence and interpret the entire exome relatively quickly, allowing a diagnosis in 25-30% or more of cases of developmental disorders when other genetic tests have not yielded a result.

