The UCSF Fresno/Community Medical Center, one of our study sites, will be enrolling patients starting in January 2020 (their own IRB was recently approved). Three of their team members will be adding data into our Redcap database directly and will therefore have access to our study identifiers. We were unable to add them to the personnel section of the study application because they are not UCSF employees, so we are adding them here as per [name]'s instructions. They team members are

[name], a study coordinator, [contact]; [name], a genetic counselor, [contact]; and [name], a genetic counselor, [contact]; [name], a genetic counselor, [contact]

7.11 INSTRUMENTS: List all questionnaires, surveys, interview, or focus group guides that will be used for this study:

We will also analyze and describe clinical interactions and experiences across prenatal and pediatric clinic settings in order to understand context and document patient-provider

interactions. These activities are part of research and are not part of clinical care. Points 1-3 below (the video recordings of clinical interactions, ethnographic observations and interviews are covered under a separate IRB protocol, 17-23118). Specifically, we will do the following:

1. Conduct detailed, ethnographic observations in each clinical setting to elucidate the full contextual experience of families offered sequencing for a potential genetic disorder identified during pregnancy (the prenatal context) or during the care of their affected infant or child (the pediatric context).
2. Follow 60 families (1/3 prenatal) who accept sequencing and conduct in-depth interviews at two time points, targeting a sample constructed to include ancestral diversity (ascertained by self-reported race/ethnicity) and social/economic status (ascertained by insurance coverage). Physicians and genetic counselors will also video record key clinical interactions. Using the constant comparative method, we will compare and contrast the experience of families. Interviews and analysis of videos will elucidate strengths and limitations of communication, revealing how families—including those from diverse, underserved backgrounds—understand genomic sequencing, its potential outcomes, and its consequences.
3. Using semi-structured interviews, assess the reasoning and experience of 60 families who are offered but refuse sequencing, including the potential impact of economic and access issues.

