Whole exome sequencing (WES) has been increasingly incorporated into laboratory genetic testing at academic and commercial laboratories. WES is aimed at detecting pathogenic sequence variants in patients with suspected genetic conditions and has become part of routine practice by Medical Geneticists, as well as an increasing number of clinicians from other medical specialties. Large case series from clinical laboratories (>2,800 patients) have confirmed the clinical validity of WES in the diagnosis of rare genetic diseases [1, 2]. Among subpopulations of patients, e.g. children with nervous system dysfunction, such as developmental delay, the diagnostic yield has been found to be as high as 41% [2]. In the Deciphering Developmental Disorders Study, which recruited >1,000 children with severe undiagnosed developmental disorders, WES combined with copy number analysis identified likely pathogenic variants in 28% of children [3]. These diagnostic yields are unprecedented and are not achievable with other testing strategies.

The purpose of WES is to identify an underlying etiology in patients with features suggestive of a genetic disorder, but without features diagnostic of a particular condition. Sequencing enables comprehensive screening that is not feasible with sequential single gene testing or gene panel testing. For individuals with rare genetic diseases, WES has proven invaluable in establishing a diagnosis, determining recurrence risk for patients and other family members, understanding prognosis, guiding therapies and health surveillance.

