10.0 Sample Size and Eligibility Criteria

10.1 ENROLLMENT TARGET: How many people will you enroll:

up to 800 families

If there are multiple participant groups, indicate how many people will be in each group:

Our enrollment goals for patients include up to 800 probands and up to 1700 biological parents or other family members.

There are no power calculations associated with this study. We chose 800 patients to maximize enrollment of pediatric patients with likely genetic diagnoses within the cost restraints of the grant. Patients will be enrolled with one or two biological parents, and in some cases with affected siblings as well.

We also estimate enrolling approximately 25 physicians who have referred patients to the study. These referring physicians, most of whom are study investigators, will be asked to complete surveys primarily meant to assess the clinical utility of exome sequencing for the patients they referred and to provide limited information about their own background.

We estimate enrolling approximately 10 administrators or clinicians at UCSF to complete the ORCA questionnaire.

10.3 SAMPLE SIZE JUSTIFICATION: Explain how and why the number of people was chosen. For multi-site studies, this is referring to the number that will be enrolled across all sites:

Our enrollment goals for patients include up to 800 probands and up to 1700 biological parents or other family members.

There are no power calculations associated with this study. We chose 800 patients to maximize enrollment of pediatric patients with likely genetic diagnoses within the cost restraints of the grant. Patients will be enrolled with one or two biological parents, and in some cases with affected siblings as well.

We also estimate enrolling approximately 25 physicians who have referred patients to the study. These referring physicians, most of whom are study investigators, will be asked to complete surveys primarily meant to assess the clinical utility of exome sequencing for the patients they referred and to provide limited information about their own background.

We estimate enrolling approximately 10 administrators or clinicians at UCSF to complete the ORCA questionnaire.

10.4 * PARTICIPANT AGE RANGE: Eligible age ranges: (REQUIRED)

- 0-6 years
- 7-12 years
- 13-17 years
- 18-64 years
- 65+

10.5 * STUDY POPULATIONS: Data will be collected from or about the following types of people (check all that apply): (REQUIRED)

- Inpatients
- Outpatients

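### The SAP's yield comparisons by race/ethnicity and socioeconomic status have no case-mix adjustment and no rule for overlapping indications

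*SAP*

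**What the plan says.** The SAP is a single paragraph. It defines diagnostic yield per proband as the "number of cases with a positive or likely positive exome result divided by the total number of cases". It then plans to study how yield, which it uses as its measure of clinical utility, varies over factors "including setting (prenatal or pediatric), by disease indication, by race/ethnicity, and by socioeconomic status". It adds one qualification: "Such stratified analyses will depend on the actual observed sample sizes within each stratum". It names no joint model, adjustment or standardisation, and it does not say how a proband is assigned to an indication stratum.

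The protocol does not fill the gap:

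- Section 7.2 recruits for a range of conditions, "including intellectual disability, seizures, encephalopathy, metabolic disease, birth defects, neurodegenerative conditions and multiple congenital anomaly syndromes". Section 7.9 describes the 80 intensive-care patients as having encephalopathy, multiple congenital anomalies, or both.
- Section 7.13 expects too few patients to justify statistical methods, and section 10.3 states that there is no power calculation.
- The blinded comparison in section 7.9 sets positive against non-positive results, which is a different question.
- Section 12.4 says that patients enter after whatever clinically appropriate genetic testing their insurance made possible. Section 10.7 allows enrolment with one or two biological parents.

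**The concern.** Two things are missing.

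The first is a coding rule. The seven labels in section 7.2 are not mutually exclusive: birth defects and multiple congenital anomaly syndromes are both listed, and one child may also have seizures and intellectual disability. Without a rule, the make-up of each indication stratum is left to be decided after the results are known.

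The second is adjustment. If yield differs by indication and the groups differ in indication mix, crude yields will differ between groups that have the same yield within every indication. The same mechanism can hide a real difference. For socioeconomic status the protocol documents a further route: work-up before entry depended on coverage, so the probands who reach sequencing may already be selected differently by insurance.

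The protocol's aim in section 7.2 is framed around minority and underserved patients. A yield gap by race/ethnicity or socioeconomic status is therefore likely to be read as a finding about equity, and the plan gives the reader no means of telling it from case mix.

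**Working it through.** The documents give no effect size, significance level or power for these comparisons, so there is no figure to reproduce. What follows illustrates the mechanism.

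**Inputs from the documents**

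- Sample size: "Our enrollment goals for patients include up to 800 probands" (section 10.1).
- Under-represented minority share: a 60% minimum (sections 7.9 and 10.7) gives 0.60 × 800 = 480 against 320; a 75% target (section 7.4) gives 0.75 × 800 = 600 against 200.
- Yields: among children with nervous-system dysfunction, "the diagnostic yield has been found to be as high as 41" per cent, and 28% in a separate cohort with severe undiagnosed developmental disorders (both section 9.4).

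**Assumptions**

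- There are two indication classes, with yields of 41% and 28%. Treating these figures as yields of two indications within one population is itself an assumption.
- A share m1 of one group and m2 of the other fall in the higher-yield class. The documents give no indication mix by group.
- There is no group effect within either class, and the test is two-sided at 0.05.

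**Gap from mix alone**

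Gap = (m1 − m2) × (0.41 − 0.28). For 70% against 40%, the crude yields are:

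- 0.70 × 0.41 + 0.30 × 0.28 = 0.371
- 0.40 × 0.41 + 0.60 × 0.28 = 0.332

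The gap is 0.30 × 0.13 = 0.039, or 3.9 points.

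**Chance that the crude test rejects**

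With d the gap, s0 the pooled and s1 the unpooled standard error, P = 1 − Φ((1.96·s0 − d)/s1) + Φ((−1.96·s0 − d)/s1).

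At 480/320 the pooled yield is 0.3554, s0 = 0.0345 and s1 = 0.0343. The first argument is (0.0677 − 0.039)/0.0343 = 0.84, so P is about 0.20.

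| Mix, m1 vs m2 | Crude gap (points) | Rejection, 480/320 | Rejection, 600/200 |
|---|---|---|---|
| 55% vs 45% | 1.3 | 6.6% | 6.2% |
| 60% vs 40% | 2.6 | 11.7% | 10.0% |
| 70% vs 40% | 3.9 | 20.3% | 16.5% |
| 70% vs 30% | 5.2 | 32.5% | 26.0% |
| 80% vs 20% | 7.8 | 62% | 51% |
| 100% vs 0% (ceiling) | 13.0 | 96.8% | 91.9% |

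**Sensitivity to the yields**

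At the 70/40 mix, 41% against 25% gives 0.30 × 16 = 4.8 points (rejection 28.7% at 480/320, 23.0% at 600/200). Assumed yields of 50% and 15% give 0.30 × 35 = 10.5 points. Equal yields give zero.

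**Does adjustment remove it?**

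The 70/40 case at 41% and 28% was simulated 4,000 times. The crude test rejected in 19% of runs at 480/320 and 17% at 600/200. A Cochran-Mantel-Haenszel test stratified by indication class rejected in 5.2% and 5.1%, with mean adjusted gaps of −0.15 and 0.03 points. The simulation uses one confounder, measured without error, so it shows the mechanism rather than what real adjustment would achieve.

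**Scale**

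The 95% interval for a gap has half-width 1.96 × √(p(1 − p)(1/n1 + 1/n2)). For p between 0.30 and 0.40 this runs from 6.5 points (480/320) to 7.8 points (600/200). Moderate mix differences thus shift the estimate by less than its own half-width.

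**The case against.** The strongest reply is that these are descriptive analyses. Crude yields by group are legitimate quantities, section 7.2 states no hypothesis about racial or socioeconomic differences, and whether to condition on indication is a choice of estimand. This stands in part, and it is why the crude yields should stay. But the SAP opens by promising statistical comparisons and does not say which estimand is meant.

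The numbers are also open to challenge. The 41% is an upper figure. The 41%, the 28% and the statement in section 7.4 about sequencing "allowing a diagnosis in 25-30% or more of cases of developmental disorders" come from different and overlapping populations, and no section gives a yield for non-neurological indications. This stands: the yield contrast is as much an assumption as the mixes.

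A reader might infer more than the text supports:

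- *That each factor is analysed strictly alone.* This is a natural reading of the parallel list, but the list is open-ended and does not exclude cross-classification. The supportable statement is that no adjustment is specified.
- *That indication strata double-count children.* The SAP does not say whether indication means the primary one or every feature. This is a missing definition, not a demonstrated error.
- *That site or timing drives a gap.* Section 7.9 says the Fresno site "will be enrolling patients starting in January 2020", and section 9.4 says interpretation is limited by the databases available. No site demographics, site yields or time trend are given. Section 7.4 describes sites that together serve a diverse population, not sites selected to contrast with one another.
- *That a large spurious gap is likely.* This needs mixes such as 80% against 20%, and nothing in the documents suggests them.

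**Conclusion.** The concern holds as a gap in specification. The SAP plans to compare yield across race/ethnicity and socioeconomic groups with no case-mix adjustment and no indication-coding rule, and the protocol supplies neither. A crude gap could therefore partly reflect indication mix or, for socioeconomic status, insurance-dependent prior testing.

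The size is illustrative. On 41% against 28% with no true group effect, a 70/40 mix gives 3.9 points and about 17-20% false rejection against a nominal 5%; a 55/45 mix gives 1.3 points and 6-7%. On those yields, mix alone cannot produce a gap above 13 points. The overlap of the labels and the dependence of testing on insurance come from the text. The yields by class, the mixes, the two-class simplification and the 0.05 level are assumptions, and the effect of prior testing cannot be sized from the documents. The documents do not show that a spurious gap will occur, only that the plan could not recognise one.

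**What to change.** Keep the crude yields by group, with intervals, as the descriptive result. Add to the SAP:

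1. A coding rule: each indication is recorded yes or no for every proband, so that labels may overlap, and any table by indication states that its rows are not exclusive.
2. One logistic model for a positive result, with race/ethnicity, socioeconomic status, a yes/no term for each indication, number of parents sampled (one or two) and prior genetic testing. Report adjusted yield differences with 95% confidence intervals by marginal standardisation.
3. A sensitivity analysis that adds recruitment site and enrolment period. They are kept out of the main model because they may be entangled with race/ethnicity and socioeconomic status.
4. A sentence on interpretation: crude differences describe the yield seen in each group; adjusted differences compare probands with similar indications and work-up.

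The data are largely in hand. Section 7.9 collects detailed phenotypes, section 12.4 has minority and socioeconomic status tabulated before entry, and section 15.13 gives access to the full medical record, from which prior testing can be coded. At the 30-40% yield anticipated in section 9.4, 800 probands give 0.30 × 800 = 240 to 0.40 × 800 = 320 positive results, enough for a model of this size. If fewer are enrolled or an indication is rare, sparse terms should be merged by a rule set in advance.

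The cost is SAP wording, some coding of prior tests, a little more analysis and somewhat wider intervals for the adjusted gaps.
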